### 11.18 Immunogenicity Assessments

Serum for determination of the presence of anti-LMN-301 antibodies will be collected on Days 1 (pre- and post-dose), 2 and 8 for the sentinel cohort and on Days 1 (pre-and post-dose), 3 or 4, 7 and 14 for the multi-dose cohort. If anti-drug antibodies are confirmed, additional testing on the samples may be performed (e.g., titer and neutralizing antibodies) to further understand the process.

Serum samples will be stored at -80°C until shipped to Lumen Bioscience (Seattle, USA) for subsequent processing and analysis. With the participant's approval, de-identified leftover samples may be stored at Lumen Bioscience indefinitely and used for future research studies related to the development of LMN-301. Detailed instructions for the collection, processing, and shipment of samples for immunogenicity analysis will be described in the study Laboratory Manual.

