**Figure 8-A Unidose Nasal Device**

Each Unidose nasal device delivers a dose of 25 mg. Detailed instructions are provided in the study Pharmacy Manual.

The total dose to be delivered will be divided equally across both nostrils, with a total of 1 actuation per nostril required for each dose, i.e., a total dose of 50 mg (See [Table 8-A](#)).

All dosing will take place in the clinical facility under the supervision of site staff.

Participants in study Part A (sentinel cohort) will be observed as in-patients for 24 hours after administration of study drug.

Participants in study Part B (multiple dose cohort) will be observed on site for 4 hours after administration of the first dose.

- Participants in Group 1 will return to the site every 3rd day (Days 4, 7 and 10) for dosing and safety monitoring
- Participants in Group 2 will return to the site every 2nd day (Days 3, 5, 7, 9 and 11) for dosing and safety monitoring
- Participants in Group 3 will return to the site daily (Days 2 to 12) for dosing and safety monitoring

Details of dose administration will be recorded in the eCRF.

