#### 10.2.1 Day 1 Inpatient

Eligible volunteers will be admitted to the research unit. The following procedures will take place on Day 1:

- Record concomitant medications before and after drug administration
- Review inclusion/exclusion criteria before dosing
- Urine pregnancy test (females of child-bearing potential only) before dosing
- COVID-19 RAT test before dosing
- Urine tox screen for drugs of abuse before dosing
- Alcohol breath test before dosing
- Collect whole blood for hematology before dosing
- Collect serum for chemistry before dosing

- Collect blood for PT, APTT INR before dosing
- Perform a targeted physical examination before dosing
- Perform a nasal examination within 1 hour before and 3 hours after drug administration
- Vital signs within 2 hours before and at 30 minutes, 1 hour and 4 hours after drug administration
- Collect serum for drug detection before and 2-hours after drug administration
- Collect serum for anti-drug antibodies before and 2 hours after drug administration
- Collect nasal mucosal lining fluid (MLF) samples before and 2-hours after drug administration
- Administer study drug by intranasal delivery to each nostril using a unidose powder device
- Perform Sino-Nasal Outcome Test at 2 hours after drug administration
- Record solicited AEs (stuffy nose, runny nose, sneezing, nasal irritation, nasal tenderness/pain, loss of smell, sore throat scratchy throat, cough) and unsolicited AEs/SAEs
- Participants will be provided with a diary (paper or electronic) to record any solicited and/or unsolicited AEs daily, and to record concomitant medication usage.

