#### 10.2.5 Day 14 Outpatient Visit (End of Study)

- Perform a targeted physical examination
- Vital signs
- Record solicited AEs and unsolicited AEs/SAEs
- Record concomitant medications
- Twelve-lead ECG
- Urine pregnancy test (WOCBP only)
- Collect whole blood for hematology
- Collect serum for chemistry
- Collect blood for PT, APTT, INR
- Urine collection for urinalysis
- Site staff to collect diary

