#### 10.3.5 Day 28 End of Study Visit

Participants will come into the research unit on Day 28 and the following procedures will take place:

- Recording concomitant medications
- Vital signs
- Twelve-lead ECG
- Perform Sino-Nasal Outcome Test
- Collect whole blood for hematology
- Collect serum for chemistry
- Collect blood for PT, APTT, INR
- Collect urine for urinalysis
- Record AEs/SAEs
- Review and collect diary
- Urine pregnancy test (females of child-bearing potential only)

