### 21.2.2 Part B (Multiple Dose)

**Table 21-D Pharmacokinetic and Immunogenicity Sampling Schedule (Part B Multiple Dose)**

Day	Timepoint	PK (blood)	PK (nasal secretions)	Immunogenicity (plasma)	Time Window
1	Pre-dose	X	X	X	Any time prior to dose administration on the day
	First Dose				
	2 hr post-dose	X	X	X	± 15 min
3 (Groups 2 & 3 only)	Pre-dose	X	X	X	Any time prior to dose administration on the day
4 (Group 1 only)	Pre-dose	X	X	X	Any time prior to dose administration on the day
7	Pre-dose	X	X	X	Any time prior to dose administration on the day
14	End of Study	X	X	X	Any time on the day of EoS visit

Abbreviations: PK = pharmacokinetic.

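### Part B stops anti-drug antibody sampling on Day 14 although the Day 28 visit already draws blood, so treatment-induced antibodies may be missed

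*Protocol*

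**What the plan says.** Detecting anti-drug antibodies in serum is part of the exploratory objective (Protocol Table 5-A; SAP Section 2.2.3).

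**Part B sampling.** Protocol Section 11.18 places the samples on Day 1 before and after dosing and on Days "3 or 4, 7 and 14 for the multi-dose cohort". Section 10.3.1 and Table 21-D put the Day 1 post-dose sample at 2 hours.

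**Part B dosing.** Under Section 8.5, Group 1 returns on "Days 4, 7 and 10) for dosing and safety monitoring". Group 2 is last dosed on Day 11 and Group 3 on Day 12.

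**Part B end of study.** Section 10.3.5 states: "Participants will come into the research unit on Day 28 and the following procedures will take place". Its list includes haematology, chemistry and coagulation samples but no ADA sample. Table 21-D nevertheless labels its Day 14 row End of Study, with the window "Any time on the day of EoS visit".

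**Part A.** Section 11.18 gives "Days 1 (pre- and post-dose), 2 and 8 for the sentinel cohort". Section 10.2.5 and Table 21-A describe Day 14 as a clinic visit with safety blood, including "Collect blood for PT, APTT, INR". Section 6.2 describes the Day 14 contact as a telephone follow-up.

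**When IgG is tested.** The synopsis and SAP Section 2.2.3 make IgG testing conditional on finding drug in serum. Protocol Table 5-A carries no such condition.

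**The concern.** An antibody response takes time to become measurable, and this schedule is concentrated at the start. Of the four post-baseline ADA samples in Part B, two fall within 3 days of first dose (2 hours, and Day 3 or 4). The 2-hour sample cannot show a response to the dose just given. Sampling then stops two weeks before the last visit, at which blood is drawn anyway.

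The protocol expects low immunogenicity (Section 4.2), and this trial is a chance to check that in people. If all samples are negative, a reader cannot tell absence of a response from a window that closed too soon. Part B adverse events are followed to Day 28, so an event after Day 14 would also have no ADA result close to it in time. Neither document gives a reason for ending ADA sampling on Day 14.

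**Working it through.** **1. The plan's own figures.** The documents give no figure for ADA detection. Two related figures reproduce.

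- Table 11-B blood volume: 24 + 54 + 18 + 9 + 20 + 20 + 10 = 155 mL, as stated. The immunogenicity row is 5 × 4 = 20 mL. The safety-laboratory rows count 6 timepoints, which matches Screening and Days 1, 3 or 4, 7, 14 and 28, so the Day 28 draw is already in the budget.
- Sample size statement (Section 13.1): for a 10% event rate and N = 30, 1 − 0.9^30 = 0.958, as stated (over 95%). This is also the most that step 4 can reach.

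**2. Intervals in Part B** (Day 1 = first dose).

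- From first dose: 14 − 1 = 13 days now; 28 − 1 = 27 days with a Day 28 sample.
- From last dose:

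| Group | Last dose | To Day 14 | To Day 28 |
|---|---|---|---|
| 1 | Day 10 | 4 days | 18 days |
| 2 | Day 11 | 3 days | 17 days |
| 3 | Day 12 | 2 days | 16 days |

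**3. Share of eventual responders detectable by day t.** Assumption, not from the documents: time from first dose to detectable IgG is log-normal with median m and log-SD 0.3, and a response stays detectable once it appears. Then F(t) = Φ[(ln t − ln m)/0.3]. For m = 14 and t = 13, ln(13/14) = −0.074; divided by 0.3 this is −0.247; Φ = 0.40.

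**4. Chance of seeing at least one responder in Part B.** With an illustrative true ADA rate of 10% and n = 30, P = 1 − (1 − 0.1 × F)^30. For m = 14 at Day 14, 1 − (1 − 0.0402)^30 = 0.708.

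| Median m (days) | Detectable by Day 14 | Detectable by Day 28 | P(at least one), Day 14 | P(at least one), Day 28 |
|---|---|---|---|---|
| 7 | 98% | 100% | 0.955 | 0.958 |
| 10 | 81% | 100% | 0.920 | 0.958 |
| 14 | 40% | 99% | 0.708 | 0.956 |
| 21 | 6% | 80% | 0.152 | 0.918 |

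The share missed at Day 14 is thus about 2%, 19%, 60% and 94%.

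**5. Part A.** The last ADA sample is 8 − 1 = 7 days after the only dose; a Day 14 sample would be at 13 days. On the same assumption the detectable shares at Day 8 versus Day 14 are 50% vs 98%, 12% vs 81%, 1% vs 40% and 0% vs 6%. With n = 5 and a 10% rate, P(at least one) cannot exceed 1 − 0.9^5 = 0.41 at any sampling time.

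Whether blood is drawn on Day 14 in Part A is itself unsettled. Sections 10.2.5 and Table 21-A say it is. Section 6.2 says telephone. Table 11-A counts 4 safety-laboratory timepoints where Table 21-A shows 5 (Screening, Days 1, 2, 8 and 14), and Table 21-E ends vital signs at Day 8.

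**6. Volume in Part B.** Moving the 2-hour ADA tube leaves the immunogenicity row at 5 × 4 = 20 mL. Adding a tube gives 155 + 4 = 159 mL. Neither needs a new visit.

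**The case against.** A reader might infer that treatment-induced antibodies are likely to be missed. For Part B the documents do not support that. They give no time to seroconversion, and with a median of 10 days or less the Day 14 sample already finds 81% or more of responders. The loss becomes large only at medians of about 14 days or longer. This objection stands, and the point is that antibodies may be missed.

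A reader might also take the 2 to 4 days after last dose as the effective window. Every dose carries the same product and exposure starts on Day 1, so the 13 days since first dose is the main interval for induction. The short gap still means that any response arising from the later doses has little time to appear, but it should not be presented as the whole window.

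Nor can it be assumed that both parts have a later visit with blood. For Part A the passages conflict, so a cost-free change there is unproven.

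Other objections carry less weight. The objective is exploratory, and no passage says that negative results will be used to claim low immunogenicity. The separate Immunogenicity Analysis Plan (SAP Section 15) could limit interpretation, but it cannot create samples that were not taken. The Table 21-D label is an editorial slip: the other sections consistently give Day 14. The conditional IgG rule is a real obstacle, because a Day 28 tube is of little use if it is never assayed.

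**Conclusion.** The point holds for Part B in moderate form. ADA sampling ends 13 days after first dose, a later visit already draws blood, no reason for stopping is given, and one tube is taken when it cannot show a response to the first dose. The gain from a Day 28 sample ranges from negligible (98% to 100% of responders detectable, median 7 days) to large (6% to 80%, median 21 days). That range rests on an assumed log-normal with log-SD 0.3, counted from first dose; the intervals and volumes rest on the documents alone.

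In Part A the 7-day window is shorter, and half or more of responders would be missed at every median tried. However, five participants can say little about ADA at any sampling time, and the change depends on resolving what happens on Day 14. Overall this is a low-severity improvement to an exploratory objective.

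**What to change.** 1. **Part B:** take an ADA sample at the Day 28 visit. Either move the 2-hour ADA tube there and keep the 2-hour drug-detection sample, or add one 4 mL tube. The first costs the 2-hour ADA value; the second costs 4 mL per participant (155 to 159 mL).
2. **Carry the change through** the protocol synopsis, Sections 6.3, 10.3.1, 10.3.5, 11.18 and 13.9, Table 11-B (if a tube is added), Tables 21-B and 21-D with their footnotes, and the SAP study description and Part B schedule (Section 2.1 and Appendix 18.2).
3. **Part A:** reconcile Section 6.2 with Section 10.2.5 and Table 21-A on the nature of the Day 14 contact. If blood is drawn then, make the same change at Day 14.
4. **Table 21-D:** correct the End of Study label and window on the Day 14 row.
5. **Testing rule:** state whether IgG is tested only if drug is found in serum (synopsis, SAP Section 2.2.3) or regardless (Table 5-A). Without this the later sample may go untested.

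The cost is a protocol amendment with matching SAP edits. SAP Section 16 indicates that participants had already been dosed when it was written. If sampling is complete, the remaining remedy is to state the 7-day and 13-day windows beside any negative ADA result in the Immunogenicity Analysis Plan and the study report.

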### 11.19 Blood Sample Volumes

The following tables contain the approximate blood volumes to be collected per participant throughout the study. The final blood volumes required for each sample type will be documented in the study Laboratory Manual.

Additional blood samples may be collected from a participant at any time throughout the study, if required for safety reasons.

**Table 11-A Approximate Blood Sample Volumes Collected Per Participant (Part 1, Single Dose) - Individual**

Sample Type	Approximate Blood Volume Per Sample	Number of Timepoints	Approximate Total Volume
Haematology	4 mL	4	16 mL
Serum chemistry	9 mL	4	36 mL
Coagulation	3 mL	4	12 mL
Serology	9 mL	1	9 mL
Serum Pregnancy	Evaluated from serum chemistry blood sample tube, where applicable.		
FSH levels			

Sample Type	Approximate Blood Volume Per Sample	Number of Timepoints	Approximate Total Volume
PK	4 mL	4	16 mL
Immunogenicity	4 mL	4	16 mL
Canula discard	2 mL	4	8 mL
Total approximate volume per participant			113 mL

Abbreviations: FSH = follicle-stimulating hormone; PK = pharmacokinetics

Note: volumes are approximate. Final blood volumes will be documented in the study laboratory manual.

**Table 11-B Approximate Blood Sample Volumes Collected Per Participant (Part 2, Multiple Dose)**

Sample Type	Blood Volume Per Sample	Number of Timepoints	Total Volume
Haematology	4 mL	6	24 mL
Serum chemistry	9 mL	6	54 mL
Coagulation	3 mL	6	18 mL
Serology	9 mL	1	9 mL
Serum Pregnancy	Evaluated from serum chemistry blood sample tube, where applicable.		
FSH levels			
PK	4 mL	5	20 mL
Immunogenicity	4 mL	5	20 mL
Canula discard	2 mL	5	10 mL
Total approximate volume per participant			155 mL

Abbreviations: FSH = follicle-stimulating hormone; PK = pharmacokinetics

Note: volumes are approximate. Final blood volumes will be documented in the study laboratory manual.

## 12 ASSESSMENT AND MANAGEMENT OF ADVERSE EVENTS

### 12.1 Adverse Event Definitions

An **AE** is any untoward medical occurrence in a patient or clinical study participant administered a pharmaceutical product and which does not necessarily have to have a causal relationship with this treatment.

An AE can therefore be any unfavourable and unintended sign (including an abnormal laboratory finding), symptom, or disease temporally associated with the use of a medicinal (investigational) product, whether or not related to the medicinal (investigational) product.

An **SAE** is any AE that at any dose:

- Results in death.
- Is life-threatening.

*Note: the term 'life-threatening' in the definition of 'serious' refers to an event in which the participant was at risk of death at the time of the event; it does not refer to an event which hypothetically might have caused death, if it were more severe).*

- Requires inpatient hospitalisation or prolongation of an existing hospitalisation.  
*Note: only hospitalisations that are longer than expected based on Investigator judgement, will be considered prolonged hospitalisations.*
- Results in persistent or significant disability/incapacity.  
*Note: results in a substantial disruption of a person's ability to conduct normal life functions.*
- Is a congenital anomaly/birth defect.  
*Note: a congenital anomaly/birth defect that occurs in the offspring of a participant exposed to the IP.*

Medical and scientific judgment should be exercised in deciding whether other situations should be considered serious such as important medical events that may not be immediately life threatening or result in death or hospitalisation but might jeopardise the participant or may require medical or surgical intervention to prevent one of the other outcomes listed in the above definition. Examples of such events are intensive treatment in an emergency room or at home for allergic bronchospasm, blood dyscrasias or convulsions that do not result in hospitalisation, or development of drug dependency or drug abuse.

**A suspected unexpected serious adverse reaction (SUSAR):** An AE that meets all the following criteria:

- Is serious
- There is at least a reasonable possibility of a causal relationship between the event and the investigational product
- Is considered unexpected (i.e., the event is not listed in the Investigator's Brochure or is not listed at the specificity or severity that has been observed). "Unexpected" as used in this definition, also refers to AEs that are mentioned in the Investigator's Brochure as occurring with a class of drugs or are anticipated from the pharmacological properties of the drug but are not specifically mentioned as occurring with the particular drug under investigation.

**Abnormal laboratory findings** (e.g., serum chemistry, haematology, coagulation, and urinalysis) **or other abnormal assessments** (e.g., vital signs, and physical examination

findings) that are judged by the PI as clinically significant (CS) will be recorded as AEs or SAEs if they meet the definitions stated above. Clinically significant abnormal laboratory findings or other abnormal assessments that are detected after the first administration of the study drug or are present at baseline and significantly worsen following administration of the study drug will be reported as AEs or SAEs. The PI will exercise his/her medical and scientific judgement in deciding whether an abnormal laboratory finding, or other abnormal assessment, is CS.

## 12.2 Evaluating Adverse Events and Serious Adverse Events

### 12.2.1 Assessment of Severity

The Investigator will make an assessment of severity for each AE and SAE reported during the study. The assessment will be based on the Investigator's clinical judgment. The severity of each AE and SAE will be graded using the most current version of the National Cancer Institute Common Terminology Criteria for Adverse Events (NCI-CTCAE) 5-point scale ([Table 12-A](#)).

**Table 12-A NCI-CTCAE 5-point Scale for Grading the Intensity of Each AE and SAE**

Grade		Definition
I	Mild	Asymptomatic or mild symptoms: clinical or diagnostic observations only; intervention not indicated.
II	Moderate	Minimal, local, or non-invasive intervention indicated; limiting age-appropriate instrumental ADL.
III	Severe	Severe or medically significant but not immediately life-threatening: hospitalisation or prolongation of hospitalisation indicated; disabling; limiting self-care ADL.
IV	Life-threatening	Life-threatening consequences: urgent intervention indicated.
V	Death	Death related to AE.

Abbreviations: ADL = activities of daily living; AE = adverse event.

If an AE/SAE has multiple aspects (symptoms), the aspect with the highest severity will be graded.

The term severe is a measure of severity. Thus, a severe AE is not necessarily serious. For example, itching for several days may be rated as severe, but may not be clinically serious.

### 12.2.2 Assessment of Causality

The Investigator will make an assessment as to the relationship between study drug and the occurrence of each AE/SAE. The Investigator will use clinical judgment to determine whether or not the AE/SAE is causally related to the study drug. Alternative causes, such as natural history of any underlying diseases, concomitant therapy, other risk factors, and the temporal relationship of the event to the study drug will be considered and investigated. The Investigator will also consult the Investigator's Brochure in the determination of his/her assessment.

The causal relationship of the study drug to an AE/SAE will be rated according to the following 2-point scale Table 12-B.

**Table 12-B Categories for Assessing Relationship of an Adverse Event to Study Drug**

Causal Relationship	Definition
Not related	Temporal association with study drug administration is lacking or other causative factors (e.g., participant's clinical state or environmental factors or other therapies administered) more likely explain the event.
Related	There is a reasonable temporal association with administration of study drug or the event is more likely explained by the investigational product than by another cause (i.e., the AE shows a pattern of response consistent with previous knowledge of the study drug).

The causality assessment is one of the criteria used when determining regulatory reporting requirements, therefore, the Investigator must make an assessment of causality based on all available information for every event and prior to transmission of an SAE Form to the Sponsor. The Investigator may change his/her opinion regarding causality in light of follow-up information and amend the SAE Form and the eCRF accordingly.

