### 6.4.2 Dose Stopping Rules

AEs which will prompt stopping the investigational product administration for all subjects and review include:

- Any individual experiencing any SAE considered at least possibly related to the investigational products; or
- If two or more subjects experience the same or similar unanticipated adverse event that is Grade 3 in severity or higher; or
- If the accumulation of SAEs and/or severe AEs collectively raises a safety concern in the opinion of the PI, Medical Monitor, or Sponsor.
- If any individual experiences liver function tests or creatinine increased to 3 times the upper limit of normal; or
- If any individual experiences significant spontaneous bleeding or platelet count  $< 100 \times 10^9/L$ ; or
- If any individual experiences coagulation disorders characterised by prolonged PT; or PTT or abnormal INR greater than 1.5 times the upper limit of normal
- If any individual experiences neutrophil values  $< 1.0 \times 10^9/L$

The decision to restart the study will be made by consensus of the Independent Medical Monitor, the sponsor's medical expert, and the Principal Investigator. The decision to stop the study will be communicated to the HREC and, similarly, the decision to re-start a study will also be communicated to the HREC.

Administration of the investigational product will be discontinued for any subject that develops:

- A serious adverse event considered at least possibly related to the investigational product; or
- An adverse event that is Grade 3 or higher and considered at least possibly related to the investigational product; or
- The Principal Investigator deems that stopping the investigational product administration is in the best interest of the subject.

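### Table 12-B's two causality categories overlap, and one limb lets an event with a reasonable possibility of drug causation be recorded as Not related

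*Protocol*

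**What the plan says.** Protocol 12.2.2 asks the investigator for a clinical judgement on causality. Other possible causes are to be weighed, and "the temporal relationship of the event to the study drug will be considered and investigated". The relationship then "will be rated according to the following 2-point scale", which is Table 12-B.

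- *Related*: "There is a reasonable temporal association with administration of study drug or the event is more likely explained by the investigational product" (against other causes).
- *Not related*: timing is lacking, or other factors (the participant's clinical state, "environmental factors or other therapies administered) more likely explain the event".

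Two other parts of the protocol use a causality threshold in different words. Section 12.1 makes a reasonable possibility of drug causation one of the criteria for a SUSAR. Section 6.4.2 has three rules that turn on an event being at least possibly related:

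- study level: "Any individual experiencing any SAE considered at least possibly related to the investigational products";
- individual level: "A serious adverse event considered at least possibly related to the investigational product";
- individual level: "An adverse event that is Grade 3 or higher and considered at least possibly related to the investigational product".

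SAP 13.1 defines treatment-related events as TEAEs recorded as *Related*, and nothing else.

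**The concern.** A two-category scale should put each event in one category. Here, an event with plausible timing and a likelier alternative explanation fits both. Section 12.2.2 names the things to weigh but does not say which definition prevails when both are met. This is a realistic case. The solicited events in section 12.3 include runny nose, sneezing, sore throat and cough, and section 12.4 itself uses that set of symptoms as an example of what may be reported as an upper respiratory infection. A participant who catches a cold during dosing produces exactly this conflict.

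The second difficulty is one of threshold. A cause can be likelier than the drug while the drug remains a reasonable possibility. Table 12-B permits *Not related* for that event, although sections 12.1 and 6.4.2 would treat the drug as implicated.

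The trial is open-label and has no control arm, so investigator causality is the main means of attributing events to LMN-301. At stake are the consistency of the recorded category from one event to the next and the completeness of the treatment-related tables. Table 12-B is followed by a statement that the causality rating feeds into regulatory reporting decisions, so the category has a use beyond the tables.

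**Working it through.** The plan gives no figure to reproduce on this point. The check is a logical one, followed by two counts.

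**Step 1. Do the definitions overlap?** Inputs are the two definitions in Table 12-B. Let timing be reasonable or lacking (treated as opposites), and let the likelier cause be the product, something else, or neither. Then:

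- *Related* = timing reasonable OR product likelier
- *Not related* = timing lacking OR other cause likelier

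| Timing | Likelier cause | *Related* met | *Not related* met |
|---|---|---|---|
| Reasonable | Product | Yes | No |
| Reasonable | Other | **Yes** | **Yes** |
| Reasonable | Neither | Yes | No |
| Lacking | Product | **Yes** | **Yes** |
| Lacking | Other | No | Yes |
| Lacking | Neither | No | Yes |

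Two of 6 combinations meet both definitions, 4 of 6 meet exactly one, and none meets neither. The second row is the practical case. The fourth is a logical overlap that should be rare.

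**Step 2. Do the thresholds agree?**

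| Place | What makes the drug implicated | Reasonable possibility, but another cause likelier |
|---|---|---|
| Protocol 12.1 (SUSAR) | A reasonable possibility of causation | Implicated |
| Protocol 6.4.2 (three rules) | At least possibly related | Implicated |
| Protocol Table 12-B | Timing or product likelier, against no timing or other cause likelier | May be recorded *Not related* |

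The table is the odd one out.

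**Step 3. Which outputs lose the event?** SAP 13.1 lists 10 overall-summary lines and 9 SOC/PT tables.

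- SOC/PT tables restricted to *Related*: treatment-related; treatment-related by severity; treatment-related serious. That is 3.
- Overall-summary lines restricted to *Related*: treatment-related; treatment-related serious. That is 2.

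A non-serious event would never appear in the serious outputs, so its loss is 3 − 1 = 2 of 9 tables and 2 − 1 = 1 of 10 lines. A serious event is lost from 3 of 9 and 2 of 10. In the outputs by relationship (one table and one line) the event stays but changes category. The all-TEAE and severity outputs are unaffected, and the AE listing shows every event with its relationship.

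**Step 4. Does a single-question definition cure it?** If *Related* means that there is at least a reasonable possibility of drug causation and *Not related* means that there is none, each event answers one yes/no question. The categories are then exclusive and exhaustive, and the threshold matches section 12.1.

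**The case against.** The best defence is that section 12.2.2 makes causality one clinical judgement. Read in full, both definitions contain the same comparison between the product and other causes, so a sensible investigator would let that comparison decide. This is a fair account of how the table may be used. It does not remove the defect: the protocol does not say that the comparison overrides timing, and *Related* offers timing alone as sufficient. If the comparison did decide, the threshold mismatch in Step 2 would become systematic.

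A reader might go further and infer that the stopping rules could fail, because an event filed as *Not related* would not halt dosing. The documents do not support that. Section 6.4.2 never refers to Table 12-B. It asks its own question at a lower threshold, so an event considered possibly related triggers the rule whatever category is recorded. There are also backstops. One study-level rule reads "If the accumulation of SAEs and/or severe AEs collectively raises a safety concern in the opinion of the PI, Medical Monitor, or Sponsor". The investigator may stop dosing in a participant's best interest, section 6.5 allows withdrawal for intolerable AEs, and section 12.5 sends all SAEs to the sponsor within 24 hours without a causality filter. The three rules also amount to two distinct triggers, since the study-level SAE rule stops dosing for everyone and so covers the individual SAE rule. The thinnest cover is for a single non-serious Grade 3 event, where the fallback is mainly the investigator's discretion.

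A reader might also wish to size the problem by the share of study days that lie close to a dose. The protocol does not define reasonable temporal association, so any such window would be invented. It would also measure timing only, whereas the practical overlap needs a likelier other cause as well.

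**Conclusion.** Table 12-B is wrong as written: two of six combinations of timing and likelier cause satisfy both categories, and no rule of precedence is given. Its limb on a likelier other cause is also inconsistent with the causality thresholds in sections 12.1 and 6.4.2.

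The consequence is minor. It reaches 2 of 9 SOC/PT tables and 1 of 10 summary lines for a non-serious event, or 3 of 9 and 2 of 10 for a serious one. All are descriptive, and the events stay visible elsewhere. The primary endpoints rest on the occurrence of AEs, discontinuation and changes from baseline, and do not depend on the causality rating. The sample-size statement is untouched, and no missed stop is demonstrated.

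The overlap follows from the wording alone, given that reasonable and lacking timing are taken as opposites. How many events would be classed differently cannot be derived from the documents.

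**What to change.** In Table 12-B, define *Related* as at least a reasonable possibility that the study drug caused the event, including when another cause is likelier, and *Not related* as no reasonable possibility. This uses the protocol's own SUSAR threshold. Requiring timing and no likelier other cause would also remove the overlap, but it would leave the mismatch with sections 12.1 and 6.4.2.

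Leave the triggers in section 6.4.2 independent of the table. Equating them with *Related* could narrow them, because a remote possibility may count as possible without being a reasonable possibility. If a link is wanted, make it one-way: any event rated *Related* counts as at least possibly related, and an event rated *Not related* still triggers the rule if the drug is considered a possible cause.

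The cost is a rewording of one table, plus an optional sentence in section 6.4.2. No new data and no SAP change are needed. The downside is that the number of events rated *Related* may rise, by an amount that the documents do not allow to be derived. SAP section 16 reads as though all enrolled participants had already been dosed. If so, the rewording helps only further dosing, and the study report should state how *Related* was applied when both definitions were met.
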